In 2012 the National Cancer Registration and Analysis Service (NCRAS) and the National Cancer Intelligence Network (NCIN) reported a pilot audit project for patients diagnosed with recurrent and metastatic breast cancer[6]. Fifteen UK breast units (out of 144) participated for 6 months in 2011. They identified 137 patients with LRR only and 114 patients with both locoregional and distant recurrences. However, this project did not investigate associated patient and tumour characteristics or evaluate the patient's initial cancer treatment. Furthermore, there was a lack of detailed analysis of treatments received by the patients diagnosed with LRR or evaluation of any variation in patient management between

participating units. Most importantly, these patients were not followed up to determine survival outcome.

Reflecting this lack of data, there is no current UK specific guideline on how breast cancer patients with LRR should be managed with little reliable data on the rate of LRR in the UK. The American National Comprehensive Cancer Network (NCCN) clinical practice guidelines in oncology[7] (BINV-19) provides recommendation as to how patients with LRR should be managed in terms of staging investigations to detect for any presence of distant metastasis, type of LRR resection surgery, management of the axilla, and types of adjuvant treatments to be offered. However, reflecting the relative lack of research in this area, the guideline acknowledges uncertainties in terms of optimal axillary management, the role of LRR resection should be utilised. Multidisciplinary approach is advocated to optimise patient outcome. However, further research is needed to gather data on tumour characteristics and treatment details of the initial and recurrent cancer, which will enable treatment recommendation for LRR to be tailored for each patient in order to achieve optimal outcome.

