Descriptive summary statistics will be calculated for each outcome and regression analysis used to control for predictive variables. Data will be tested for distribution and differences between groups using unpaired t-tests, Mann-Whitney U tests and Chi squared tests as appropriate. Based on the NCRAS report described in section 1, approximately 250 patients were diagnosed with LRR with or without distant metastasis across 15 UK breast units over 6 months. This data suggests that around 33 patients will be eligible for recruitment over 12 months in each breast unit. This potential sample size has been corroborated from data at Leeds Teaching Hospitals NHS trust (LTHT) where 28 patients met the eligibility criteria (January 2019 to December 2019). This was based on information from the LTHT cancer information team. There are 144 breast units in the UK and at least 50 units so far have agreed to participate in the study. Given the variable number of cancer patients treated per year in these participating units, we would anticipate each unit to recruit 5 to 10 patients over 12 months. Therefore, we would aim to recruit at least 500 patients diagnosed with LRR +/distant metastasis over 24 months. There are no statistical criteria for stopping the study early as the study is observational in nature examining current UK practice and therefore low risk.

One of the key aim of the study is to determine whether patient prognosis after their LRR diagnosis (without distant metastasis) differs according to the type of breast cancer surgery (mastectomy versus BCS and radiotherapy) for the initial cancer. Based on published studies[36, 37, 39], the distribution of patients presenting with LRR is almost even between mastectomy and BCS for the initial cancer (40% mastectomy and 60% BCS). From these published studies, the 5 year DFS after treatment for LRR has been reported to be approximately 70%[67, 68]. A single centre retrospective study by Shenouda *et al*[39] identified that patients initially treated with BCS and radiotherapy had improved DFS by

approximately 20% as compared to patients initially treated with mastectomy and no radiotherapy (5 year DFS of 80% vs. 60%).

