Power calculation was performed to determine sample size in each group (patients treated with mastectomy versus BCS and radiotherapy for the initial cancer), using logistic regression analysis to adjust for other covariates stated in the background section (tumour and nodal staging, molecular receptor profile, and tumour grade). This calculation has determined that the estimated sample size for each group would be 165 patients. Therefore, a subset of 330 patients diagnosed with LRR without distant metastasis will require recruiting to the study to determine whether patient prognosis differs according to the type of breast cancer surgery performed for the initial cancer. This falls well within the minimum patient recruitment target of 500 patients who are diagnosed with LRR +/- distant metastasis.

Kaplan Meier survival analysis will be performed at the two study time points (3 and 5 years after diagnosis of LRR). We will determine DFS/PFS/OS for the study participants. DFS will be determined for patients diagnosed with LRR without associated distant metastasis at presentation who then subsequently undergo LRR resection. PFS will be determined for patients diagnosed with LRR with associated distant metastasis at presentation. OS will be determined for the whole study cohort (i.e. patients diagnosed with LRR with or without associated distant metastasis at presentation). We will perform Cox proportional hazards regression for multivariate analysis and log-rank tests for univariate analysis, including potential prognostic factors as variables of interest.

9. Publication and authorship policy

All presentations and publications will be made on behalf of the MARECA study steering group. The steering group will be responsible for drafting manuscripts and preparing them for publication. Three levels of authorship are proposed based on degree of study participation:

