Thank you very much for taking time to complete the survey. We are in the process of setting up a national study of **ma**nagement of breast cancer locoregional **re**currence and oncologi**ca**l outcome (the MARECA study). We welcome participation from all UK breast units. Please email the study team ([contact]) to register your interest. We especially welcome participation from trainees.

MARECA study Gantt chart

021	2022	2023	2024	2025	2026	2027	2028	2029	203
			_				_		
MARECA study national practice questionnaire Opened Feb 2021 with 41/60 study centres already completing the survey. Due to complete data return for all units by Aug 2021.	MARECA study national prospective cohort study 60 UK study centres to recruit patients newly diagnosed with breast cancer locoregional recurrence +/- distant metastasis for 24 months. Target recruitment of 500 patients. 330 patients required to determine the study's primary endpoint.			Determination of oncological outcome for the study cohort Study centres to return oncological outcome data at 3 and 5 year follow up.				222 C	
Study submitted for ethics application via IRAS: LTHT study sponsor.	NIHR portfolio adoption and study set up	Data validation and collation for analysis	Oncological outcome data collation and analysis		to / c	Collation of tissue/slide conse to design translational sub-stu / develop national guidelines with ABS		ub-stud	
Nati	ication 1: onal practice tionnaire results	Publication 2: Study Protocol	Results			l outcome o rt / identific	outcome of the / identification

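### On the protocol's only metastatic split, the minimum of 500 recruits yields about 273 patients without distant metastasis, so the 330 needed for the primary comparison does not fall well within it

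*Protocol*

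**What the plan says.** Section 8 (Sample size and data analysis) builds recruitment on the national pilot audit: "approximately 250 patients were diagnosed with LRR with or without distant metastasis across 15 UK breast units over 6 months". It then scales this down: "we would anticipate each unit to recruit 5 to 10 patients over 12 months", and concludes that "we would aim to recruit at least 500 patients diagnosed with LRR", with or without metastasis, over 24 months.

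For the comparison by original surgery it expects "40% mastectomy and 60% BCS" and 5-year disease-free survival of 80% versus 60%. After covariate adjustment, "the estimated sample size for each group would be 165 patients", which it doubles to 330 patients without distant metastasis. It closes the argument with "This falls well within the minimum patient recruitment target of 500 patients who are diagnosed with LRR +/- distant metastasis".

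The Gantt chart in the Appendix repeats the target of 500, lists 60 centres, and states "330 patients required to determine the study's primary endpoint".

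Section 1.1 gives the composition of the same pilot audit: "They identified 137 patients with LRR only and 114 patients with both locoregional and distant recurrences". Section 2.4.1 and the end of Section 8 limit the primary endpoint to patients without metastasis who have the recurrence resected.

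**The concern.** The sentence sets a subset (no distant metastasis) against a whole (with or without metastasis) and applies no fraction. Section 8 takes the audit's total but not its split, although Section 1.1 shows nearly half of those patients had distant disease. It also turns 165 per group into 330 as if the groups were equal, just after stating a 40:60 split.

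The routine reports in Section 7.3 count patients recruited, not patients in the primary comparison. A steering group that sees 500 recruits and relies on this sentence would believe the primary comparison had its stated size when it probably did not.

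**Working it through.** **Inputs.** Recruits: 500 minimum (Section 8). Without distant metastasis: 137 of 137 + 114 = 251 (Section 1.1). Surgery split: 40% mastectomy, 60% breast conserving surgery (BCS) (Section 8). Required: 165 per group (Section 8). Disease-free survival: 80% versus 60% (Section 8).

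**1. The plan's own figures.** 2 × 165 = 330 reproduces. The 165 does not, because significance level, power and covariate inflation are not given. For 80% versus 60% at two-sided 5%, the unadjusted size is 82 per group at 80% power and 109 at 90%. Reaching 165 needs a variance inflation 1/(1 − R²) with R² of about 0.51 or 0.34 respectively.

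**2. Non-metastatic yield.** 137/251 = 0.546, exact 95% confidence interval 0.482 to 0.609.
- 500 × 0.546 = 273 (241 to 304 over the interval).
- Shortfall: 330 − 273 = 57, which is 17% of 330.
- Share needed: 330/500 = 66%, above the whole interval.
- Recruits needed: 330/0.546 = 605.

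**3. Unequal groups.** 330 × 0.40 = 132 and 330 × 0.60 = 198, not 165 each. Groups of a and b carry about the information of two equal groups of n_eff = 2ab/(a + b).
- 132 and 198: n_eff = 158.4.
- To match 165 at 40:60: 2 × 0.4 × 0.6 × N = 0.48N = 165, so N = 344 non-metastatic patients, or 344/0.546 = about 630 recruits.

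**4. Groups at 500 recruits.** 273 × 0.40 = 109 mastectomy and 273 × 0.60 = 164 BCS, so n_eff = 2 × 109 × 164/273 = 131.

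**5. Power.** Power = Φ((1.96 + z_power) × √(n_eff/165) − 1.96), two-sided 5% assumed.

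| Groups | n_eff | If 165 was sized for 80% | If sized for 90% |
|---|---|---|---|
| 165 / 165 | 165 | 80% | 90% |
| 132 / 198 | 158.4 | 78% | 89% |
| 109 / 164 | 131 | 70% | 82% |

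A two-proportion calculation with the same implied inflation gives 71% and 83% for the last row. With no covariate inflation, 109 versus 164 has about 95% power for 60% versus 80%.

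**6. Above the minimum.** 50 units × 5 to 10 per year × 2 years = 500 to 1000 recruits. With the Gantt chart's 60 centres the lower end is 60 × 5 × 2 = 600, giving 600 × 0.546 = 327.5 non-metastatic patients. At 1000 recruits the figure is 546, or about 218 and 327.

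**The case against.** **The target is a floor.** Section 8 says at least 500, its range runs to 1000, and no rule in the protocol closes recruitment at 500. With 60 centres even the low rate brings the non-metastatic count almost to 330. This stands, and it means 330 is plausibly reachable. It does not rescue the sentence, which refers to the minimum, nor the Gantt chart, which also gives 500 as the target.

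**The pilot split is not a planning assumption.** It comes from 15 units over six months in 2011 and counts diagnosed patients, not consented recruits. Section 1.1 does not say whether all 114 would meet the criterion in Section 4.6.1 of no previous metastatic disease. This also stands, so 273 is an assumption-based figure with a range. It is still the only split offered, from a source Section 8 accepts for volume. For the share to reach 66%, the metastatic count would have to fall to 70 (137/207 = 66.2%), a drop of 44 from 114.

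**Stronger readings a reader might infer.**
- That 165 mastectomy patients are indispensable, so 165/0.40 = 413 non-metastatic patients and about 756 recruits are needed. A larger BCS group offsets a smaller mastectomy group; equivalent information needs about 344 and 630. The 40:60 split alone costs 1 to 2 power points.
- That BCS patients without radiotherapy must also be subtracted. Section 1.3 gives the same 60% as BCS with radiotherapy, so no separate loss should be assumed.

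**Conclusion.** The feasibility statement is unsupported by the protocol's own figures and should be corrected (should-fix). At the minimum target the expected non-metastatic count is about 273, 17% below 330, and the shortfall persists across the confidence interval of the pilot split. The metastatic share drives the problem; the unequal groups add little. Restriction to resected patients lowers the count further, by an amount the protocol does not give.

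This does not show that the study is underpowered. The figures of 70% and 82% are conditional on a two-sided 5% test and on 165 having been sized for 80% or 90% power, none of which is stated. The unadjusted comparison at the stated effect keeps about 95%. Recruitment within the protocol's expected range could also deliver the 330. The conclusion rests on 137 of 251 being a fair guide to the recruited mix.

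**What to change.** In Section 8:
- Delete the statement that 330 lies well within the minimum target.
- State the assumed non-metastatic fraction with its range (54.6%, 48.2% to 60.9%, if the pilot is used).
- Give the expected group sizes at 500 recruits (about 109 and 164) and across the expected recruitment range.
- Restate the power or detectable difference for the 40:60 split, giving the significance level, power and covariate inflation behind the 165.
- Note that only resected patients count.

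Align the Gantt chart entry. Add to the steering-group report in Section 7.3 the running count of non-metastatic, resected patients by original surgery.

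The cost is a rewrite of two paragraphs and one chart entry, plus one line in an existing report. The stated power may look less favourable. No extra patients are required, and nothing in patient care changes.

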4.2 National prospective cohort study

All UK breast units will be invited to participate through ABS, MFAC, and BCTRCG. The study will also be included in the iBRA-NET research portfolio (https://www.ibra-net.com/mareca). The study will be rolled out nationally for 24 months from November 2021 with the aim of recruiting consecutive eligible patients diagnosed with LRR +/- DM in at least 50 participating UK breast units. The study has been designed to collect information about tumour characteristics and treatment details for the patient's original and recurrent cancer. The study aim is to determine long term prognosis in patients diagnosed with LRR, which will require patient consent. Therefore, ethical approval will be (www.Hra-

decisiontools.org.uk/research) sought to include all participating centres via the Integrated Research Application System (IRAS).

A unit trainee lead will act as an associate principal investigator (pending application outcome for NIHR CRN portfolio status), who will be supervised by the principal investigator (PI, either consultant breast surgeon or oncologist) for each unit. For units without trainees, a designated member of the Clinical Research Network (CRN) research team will act in this role. The PIs will therefore have support in order to recruit and consent eligible patients to the study, as well as complete the Case Report Form (CRF) in order to determine;

- Modality of radiological staging investigations used and determination of the rate of detection of distant metastasis.
- Proportion of patients undergoing repeat breast conserving surgery for in breast recurrence.
- Proportion of patients undergoing repeat sentinel lymph node biopsy, techniques used, and their success rate in terms of sentinel lymph node re-identification.
- Adjuvant treatment modalities used to treat the LRR.
- Proportion of patients undergoing breast surgery for locoregional recurrence in the presence of distant metastasis.

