4.4 Oncological outcome evaluation

Given that trainees rotate regularly to different hospitals within their respective deaneries, the latter phase of the study examining oncological outcomes at 3 and 5 years will be led by the consultant principal investigators with support from the local research nurses and clinical trial assistants. The following information will be sought from the participating units;

Oncological outcome dataset at 3 and 5 years after LRR diagnosis

-Patient Alive? (Yes/No)

-If No, was it related to breast cancer? (Yes/No; If No what was the cause of death)

-Date of death

-Any further LRR +/- distant metastasis

-Date of further LRR

-Date of distant metastasis

Collection of the above data will enable determination of the patient's disease free survival (DFS), disease specific survival (DSS), progression free survival (PFS), and overall survival (OS). We would not anticipate direct patient contact for study purpose during this follow up period. In cases where the required information is missing or unclear, the research team may contact the patient or their General Practitioner via telephone.

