4.6 Patient inclusion and exclusion criteria

4.6.1 Inclusion criteria

- Female or male patients more than 18 years old. Treated for previous unilateral or bilateral breast cancer (invasive cancer including all histological subtypes as well as ductal carcinoma in situ) with curative intent.
- No previous evidence of distant metastatic disease.
- Recently (within the last 6 months) diagnosed with new ipsilateral breast cancer locoregional recurrence (biopsy proven invasive cancer including all histological subtypes or ductal carcinoma in situ) +/- distant metastasis.
- Able to provide written informed consent.
- A *minimum of 3 months interval* between the resection surgery for the original cancer and the diagnosis of locoregional recurrence. There will be *no maximum interval time period*.

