Study data will be collected and managed using REDCap electronic data capture tools hosted at University of Manchester and made freely available to research collaboratives in the UK. REDCap (Research Electronic Data Capture) is a secure, web-based application designed to support data capture for research studies, providing 1) an intuitive interface for validated data entry; 2) audit trails for tracking data manipulation and export procedures; 3) automated export procedures for seamless data downloads to common statistical packages; and 4) procedures for importing data from external sources. More information about the consortium and system security can be found at http://www.projectredcap.org/.

The local PI will keep a secure record of the RedCap ID with corresponding NHS number (in England Wales), Community Health Index number (in Scotland), or Health and Care number (in Northern Ireland). This is required for the research team at each participating centres (Consultant PI, research nurse, and clinical trial assistants) to access the hospital electronic system at 3 and 5 years after LRR diagnosis to record the oncological outcome as specified in section 4.4.

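### Timing the first outcome return at each patient's own 3-year anniversary, rather than at one common date, leaves about 18 of 82 available DFS events out of the first log-rank and Cox analysis

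*Protocol*

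**What the plan says.** Section 4.2 sets the accrual period: "The study will be rolled out nationally for 24 months from November 2021". Section 4.6.1 lets patients enter some time after diagnosis: "Recently (within the last 6 months) diagnosed with new ipsilateral breast cancer locoregional recurrence".

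Section 4.4 lists the outcome items under "Oncological outcome dataset at 3 and 5 years after LRR diagnosis". The items include dates of death, further LRR and distant metastasis, but no date on which the patient was last known to be alive or event-free. Section 7 has the site team "access the hospital electronic system at 3 and 5 years after LRR diagnosis to record the oncological outcome", and the Gantt chart in the appendix repeats the schedule: "Study centres to return oncological outcome data at 3 and 5 year follow up". The look-up is a records exercise; section 4.4 adds that "We would not anticipate direct patient contact for study purpose during this follow up period".

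Section 8 places the analyses at the same two points ("Kaplan Meier survival analysis will be performed at the two study time points (3 and 5 years after diagnosis of LRR") and names the methods: "We will perform Cox proportional hazards regression for multivariate analysis and log-rank tests for univariate analysis". No common data cut-off date is given anywhere.

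**The concern.** The precision of a log-rank test or Cox model depends on the number of events. If a patient's first return is made at that patient's own 3-year anniversary, anything that happens to the patient afterwards is unknown until the second return. A full-cohort 3-year analysis cannot be completed until the last recruit reaches 3 years. By then the earliest recruits have been followed in routine care for about 5 years, and their events in years 3 to 5 are already in the hospital record.

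The first comparison of BCS and radiotherapy with mastectomy, and the first prognostic-factor models, would therefore be run on fewer events than the same number of look-ups could supply. The protocol itself fixes this schedule. An SAP written later could set censoring rules, but it could not restore follow-up that sites were never asked to return.

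**Working it through.** **Inputs from the protocol**
- 330 patients for the primary comparison (section 8).
- Overall 5-year DFS of about 70%; 80% for BCS and radiotherapy vs 60% for mastectomy (section 8).
- Expected split 60% BCS, 40% mastectomy, i.e. 198/132 (section 8).
- Recruitment over 24 months (section 4.2).

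**Assumptions, not in the protocol**
- Constant hazard and even recruitment.
- Complete capture of events, with no loss to follow-up.
- Two-sided 5% test; section 8 gives neither the significance level nor the power.

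The planned 165 per group cannot be reproduced without those missing inputs. Unadjusted, 80% vs 60% at two-sided 5% needs 82 per group for 80% power and 109 for 90%. Nothing below depends on this.

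**Step 1: events at the first analysis, 70% 5-year DFS**
- Hazard: λ = −ln(0.70)/5 = 0.0713 per year.
- Everyone observed to 3 years: 1 − exp(−3λ) = 19.3%; × 330 = 63.6 events.
- Common date when the last recruit reaches 3 years, follow-up uniform on 3 to 5 years: 1 − [exp(−3λ) − exp(−5λ)]/(2λ) = 1 − (0.8073 − 0.7000)/0.1427 = 24.8%; × 330 = 81.7 events.
- Difference: about 18 events, an increase of about 28%. No follow-up exceeds 5 years.

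**Step 2: the same with the protocol's group-specific figures (80% vs 60%)**

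| Split | Own anniversary | Common date | Gain |
|---|---|---|---|
| 165/165 | 64.2 | 82.1 | 17.9 (28%) |
| 198/132 | 59.7 | 76.4 | 16.8 (28%) |

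**Step 3: power at the first analysis, unadjusted**

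Formula: Φ(|ln HR| × √(d × 0.6 × 0.4) − 1.96), with d the number of events.
- Protocol's effect: HR = ln 0.80/ln 0.60 = 0.437, |ln HR| = 0.828. With d = 63.6 power is 90%; with d = 81.7 it is 96%. Using the Step 2 counts it is 88% vs 94% (198/132) and 91% vs 96% (165/165).
- HR 0.60, an illustrative value of this review: 51% vs 62%.

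**Step 4: sensitivity of the event gain (165/165, 80% vs 60%)**
- Weibull shape 0.5 (hazard falling steeply): 80.1 to 90.1, +12%. Shape 0.7: 73.4 to 86.8, +18%. Shape 1.2: 58.7 to 79.1, +35%.
- Diagnosis dates spread over 30 months, the most that the 6-month entry window allows. One fifth of patients (0.5/2.5 years) are then past 5 years at the common date. Censored at 5 years, the common date gives 0.8 × 82.1 + 0.2 × 99.0 = 85.5 events. If the plan used the 5-year returns already made by that fifth, it would have 0.8 × 64.2 + 0.2 × 99.0 = 71.2, so the gain is 14.3 events (20%).

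**Step 5: the final analysis**
- Everyone to 5 years: 330 × 30% = 99 events, identical whether the first return was rolling or at a common date.
- Only moving the second return to a common date as well, with follow-up of 5 to 7 years, would add events: 330 × 34.8% = 115, or 107 if the hazard halves after year 5. That is 8 to 16 more. At HR 0.437 power moves from about 98% to about 99%.

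**The case against.** The strongest reply is that a fixed horizon is a legitimate choice. Objective 2(iii) in section 2.3 asks for outcomes at 3 and 5 years, every relevant section uses those two points consistently, and the sample size in section 8 rests on 5-year proportions. This stands: the protocol neither contradicts itself nor states anything wrongly, and the point is one of efficiency.

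A reader might infer that follow-up is lost for good. The documents do not support that for the first five years. Section 4.4 records event dates, so an event in year 4 is picked up at the 5-year look-up and the final analysis contains it.

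A reader might also infer that the primary comparison is left short of power. At the design effect, unadjusted power is about 90% even at the first analysis and about 98% at the final one. The drop to 51% appears only at HR 0.60, which is not in the protocol. Smaller effects are still plausible, since section 1.3 cites randomised data with nearly equal 5-year survival (58% vs 59%), and adjusted models have less precision than these figures suggest.

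Finally, a reader might conclude that follow-up to 7 years is available at no cost. Section 10.1 describes consent and record linkage in terms of the 3- and 5-year points, relapse may be recorded less completely after year 5, and the dataset has no date last known event-free, so a missed relapse could be counted as event-free time. That extension is a trade-off.

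It is also true that no section says the 3-year analysis waits for the last recruit. That follows only if the whole cohort is to have its 3-year return.

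**Conclusion.** The point holds for the first analysis only, as a minor improvement in efficiency. Under a constant hazard the anniversary schedule leaves out 17 to 18 DFS events that would already have occurred within the planned 5-year window, so the analysis uses about 64 rather than 82 (60 rather than 76 with the 198/132 split). Power at the protocol's effect is about 6 percentage points lower than it could be. The event gain shrinks to about 12% if the hazard falls steeply.

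The figures assume even recruitment, complete record capture and a full-cohort 3-year analysis. They concern the log-rank and Cox analyses. The Kaplan-Meier estimates at 3 and 5 years are unaffected, and so is the final analysis.

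**What to change.** In sections 4.4, 7 and 8, and in the Gantt chart line on returns:
- Time the first return for all patients at all units on one common cut-off date, when the last recruit reaches 3 years after LRR diagnosis.
- Record status and event dates up to that date, and add the date last known alive and event-free to the section 4.4 dataset.
- Censor at 5 years, use all of this follow-up in the log-rank and Cox analyses, and still read 3-year DFS, PFS and OS from the curves.
- Leave the second return at 5 years.

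Cost: a wording amendment and one extra data item. Each patient still has two look-ups, and a full-cohort 3-year analysis is no later than now. Early recruits' first return comes up to two years later, and units face all first returns at once instead of spread over two years.

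Extending the second return beyond 5 years is optional. It would add about 8 to 16 events and about one point of power at the design effect. It should be considered only after checking that consent and approvals cover it and that relapse after year 5 is recorded reliably.
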